3.2.2 Second Primary Cancer Reporting Requirements

All cases of second primary cancers, including acute myeloid leukemia (AML) and myelodysplastic syndrome (MDS), that occur following treatment on NCI-sponsored trials must be reported to ECOG-ACRIN using Medidata Rave

- **A second malignancy is a cancer that is UNRELATED to any prior anti-cancer treatment (including the treatment on this protocol). Second malignancies require ONLY routine reporting as follows:**

1. Complete a Second Primary Form in Medidata Rave within 14 days.
2. Upload a copy of the pathology report to ECOG-ACRIN via Medidata Rave confirming the diagnosis.
3. If the patient has been diagnosed with AML/MDS, upload a copy of the cytogenetics report (if available) to ECOG-ACRIN via Medidata Rave.

- **A secondary malignancy is a cancer CAUSED BY any prior anti-cancer treatment (including the treatment on this protocol). Secondary malignancies require both routine and expedited reporting as follows:**

1. Complete a Second Primary Form in Medidata Rave within 14 days
2. Report the diagnosis via CTEP-AERS at <http://ctep.cancer.gov>
Report under a.) leukemia secondary to oncology chemotherapy, b.) myelodysplastic syndrome, or c.) treatment related secondary malignancy
3. Upload a copy of the pathology report to ECOG-ACRIN via Medidata Rave and submit a copy to NCI/CTEP confirming the diagnosis.
4. If the patient has been diagnosed with AML/MDS, upload a copy of the cytogenetics report (if available) to ECOG-ACRIN via Medidata Rave and submit a copy to NCI/CTEP.

NOTE: The Second Primary Form and the CTEP-AERS report should not be used to report recurrence or development of metastatic disease.

NOTE: If a patient has been enrolled in more than one NCI-sponsored study, the Second Primary Form must be

submitted for the most recent trial. ECOG-ACRIN must be provided with a copy of the form and the associated pathology report and cytogenetics report (if available) even if ECOG-ACRIN was not the patient's most recent trial.

NOTE: Once data regarding survival and remission status are no longer required by the protocol, no follow-up data should be submitted via CTEP-AERS or by the Second Primary Form.

Rev. 7/16
Rev. Add18

3.3 Comprehensive Adverse Events and Potential Risks List (CAEPR) for GDC-0032 (Taselisib, NSC 778795)

The Comprehensive Adverse Events and Potential Risks list (CAEPR) provides a single list of reported and/or potential adverse events (AE) associated with an agent using a uniform presentation of events by body system. In addition to the comprehensive list, a subset, the Specific Protocol Exceptions to Expedited Reporting (SPEER), appears in a separate column and is identified with bold and italicized text. This subset of AEs (SPEER) is a list of events that are protocol specific exceptions to expedited reporting to NCI (except as noted below). Refer to the 'CTEP, NCI Guidelines: Adverse Event Reporting Requirements' http://ctep.cancer.gov/protocolDevelopment/electronic_applications/docs/aeGUIDE_lines.pdf for further clarification. *Frequency is provided based on 910 patients.* Below is the CAEPR for GDC-0032 (taselisib).

NOTE: If an AE meets the reporting requirements of the protocol, and it is listed on the SPEER, it should ***ONLY*** be reported via CTEP-AERS if the grade being reported exceeds the grade listed in the parentheses next to the event in the SPEER.

Version 2.2, October 11, 2018¹

| Adverse Events with Possible Relationship to GDC-0032 (taselisib) (CTCAE 5.0 Term) [n= 910] | | | Specific Protocol Exceptions to Expedited Reporting (SPEER) |
|---|------------------------|------------------------|---|
| Likely (>20%) | Less Likely (<=20%) | Rare but Serious (<3%) | |
| GASTROINTESTINAL DISORDERS | | | |
| | Abdominal pain | | |
| | Colitis | | Colitis (Gr 2) |
| Diarrhea | | | Diarrhea (Gr 3) |
| | Dyspepsia | | |
| | Mucositis oral | | Mucositis oral (Gr 3) |
| Nausea | | | Nausea (Gr 2) |
| | Vomiting | | Vomiting (Gr 2) |
| GENERAL DISORDERS AND ADMINISTRATION SITE CONDITIONS | | | |
| Fatigue | | | Fatigue (Gr 2) |
| | Fever | | |
| INFECTIONS AND INFESTATIONS | | | |
| | Infection ² | | |
| INVESTIGATIONS | | | |
| | Weight loss | | |
| METABOLISM AND NUTRITION DISORDERS | | | |
| | Anorexia | | Anorexia (Gr 2) |
| Hyperglycemia | | | Hyperglycemia (Gr 3) |
| RESPIRATORY, THORACIC AND MEDIASTINAL DISORDERS | | | |
| | Pneumonitis | | |

| Adverse Events with Possible Relationship to GDC-0032 (taselisib) (CTCAE 5.0 Term) [n= 910] | | | Specific Protocol Exceptions to Expedited Reporting (SPEER) |
|---|--|------------------------|---|
| Likely (>20%) | Less Likely (<=20%) | Rare but Serious (<3%) | |
| SKIN AND SUBCUTANEOUS TISSUE DISORDERS | | | |
| | Alopecia | | |
| | Dry skin | | |
| | Skin and subcutaneous tissue disorders - Other (rash) ³ | | Skin and subcutaneous tissue disorders - Other (rash)³ (Gr 2) |

¹This table will be updated as the toxicity profile of the agent is revised. Updates will be distributed to all Principal Investigators at the time of revision. The current version can be obtained by contacting [contact]. Your name, the name of the investigator, the protocol and the agent should be included in the e-mail.

²Infections, including serious infections, includes all 75 sites of infection under the INFECTIONS AND INFESTATIONS SOC.

³Rash may include rash, rash erythematous, rash follicular, rash generalized, rash macular, rash maculopapular, rash maculovesicular, rash morbilliform, rash papular, rash papulosquamous, rash pruritic, rash pustular, and rash vesicular.

Adverse events reported on GDC-0032 (taselisib) trials, but for which there is insufficient evidence to suggest that there was a reasonable possibility GDC-0032 (taselisib) caused the adverse event:

BLOOD AND LYMPHATIC SYSTEM DISORDERS - Anemia

EAR AND LABYRINTH DISORDERS - Vertigo

GASTROINTESTINAL DISORDERS - Constipation; Dry mouth; Dysphagia; Enterocolitis; Gastrointestinal disorders - Other (Crohn's disease); Oral pain; Rectal fistula

GENERAL DISORDERS AND ADMINISTRATION SITE CONDITIONS – Death NOS

INVESTIGATIONS - Alanine aminotransferase increased; Aspartate aminotransferase increased; Cholesterol high; Lymphocyte count decreased; Neutrophil count decreased; White blood cell decreased

METABOLISM AND NUTRITION DISORDERS - Dehydration; Hypokalemia

MUSCULOSKELETAL AND CONNECTIVE TISSUE DISORDERS - Muscle cramp; Myalgia

NERVOUS SYSTEM DISORDERS - Dizziness; Dysgeusia; Headache; Nervous system disorders - Other (neuropathy peripheral); Stroke

PSYCHIATRIC DISORDERS - Psychiatric disorders - Other (mood altered)

RENAL AND URINARY DISORDERS - Acute kidney injury

RESPIRATORY, THORACIC AND MEDIASTINAL DISORDERS - Cough; Respiratory failure

SKIN AND SUBCUTANEOUS TISSUE DISORDERS - Erythema multiforme; Erythroderma; Pruritus

NOTE: GDC-0032 (Taselisib) in combination with other agents could cause an exacerbation of any adverse event currently known to be caused by the other agent, or the combination may result in events never previously associated with either agent.

3.4 Dose Modifications

All toxicity grades below are described using the NCI Common Terminology Criteria for Adverse Events (CTCAE) version 4.0.

All appropriate treatment areas should have access to a copy of the CTCAE version 4.0. A copy of the CTCAE version 4.0 can be downloaded from the CTEP website (<http://ctep.cancer.gov>).

The side effects observed with GDC-0032 (taselisib) are consistent with those observed with other PI3K inhibitors. Selected toxicities of interest for GDC-0032 (taselisib) include gastrointestinal toxicities, pneumonitis, rash, stomatitis, and hyperglycemia and these are described in detail below. Certain adverse events (e.g., rash, colitis, and pneumonitis) may also occur within 4 weeks of holding or stopping GDC-0032 (taselisib).

The GDC-0032 (taselisib) dose reduction instructions provided in **Table 1** are intended to serve as recommended guidelines to allow ongoing treatment for patients experiencing clinical benefit without signs or symptoms of progression while monitoring patient safety. The investigator may temporarily suspend GDC-0032 (taselisib) dosing for up to 28 days from the last scheduled dose due to a GDC-0032 (taselisib)-related toxicity or an unanticipated medical event not associated with study treatment toxicity or with disease progression. Depending on the nature and the severity of the GDC-0032 (taselisib)-related toxicity, the investigator may resume GDC-0032 (taselisib) dosing in the patient at the same dose or at one dose level lower (as detailed in Tables 2–6).

Table 1 Overall Dose Modification Guideline for GDC-0032 (taselisib)-Related Adverse Events

| | GDC-0032 (taselisib) |
|------------------|----------------------------|
| Starting dose | 4 mg daily |
| First reduction | 2 mg daily |
| Second reduction | 2 mg every other day (QOD) |

No dose reduction is allowed for patients treated at a dose of GDC-0032 (taselisib) of 2mg QOD – if there is an indication for further dose reduction, the patient must permanently discontinue GDC-0032 (taselisib). Dose re-escalation is not allowed after a dose reduction.

NOTE: Due to the approximately 40 hour half-life for GDC-0032 (taselisib), investigators should consider holding GDC-0032 (taselisib) for certain Grade 2 toxicities until the adverse events resolves to Grade \leq 1 as discussed below (e.g., stomatitis/oral mucositis, rash, diarrhea). In addition, certain toxicities can occur or worsen within 1–2 weeks of holding or discontinuing GDC-0032 (taselisib) (e.g., pneumonitis, colitis, rash). Investigators should follow management guidelines for toxicities as described below including administration of topical or systemic corticosteroids as appropriate.

Management of Hyperglycemia

Metformin is the first antihyperglycemic medication of choice because of the lower risk of hypoglycemia with this agent. Because metformin in some patients

may also cause diarrhea and can be poorly tolerated, other antihyperglycemic medications such as sulfonylureas (e.g., glimepiride, glipizide) can be used. Extra caution should be used with other drugs such as sulfonylureas because of the increased risk for hypoglycemia with these agents. Consultation with an endocrinologist can be helpful in managing hyperglycemia. Management guidelines for fasting patients with hyperglycemia are listed below in Table 2

Table 2: Management of Hyperglycemia

| Grade | Intervention | Dose Adjustment |
|--|---|---|
| 1 | Initiation of an oral anti-hyperglycemic agent (e.g., metformin) and additional glucose monitoring should be considered. | No change. |
| 2 | Initiation or increased dose of an oral anti-hyperglycemic agent (e.g., metformin) and additional glucose monitoring should be considered. | Dosing with GDC-0032 (taselisib) may either be held or continued per Investigator evaluation. |
| 3, asymptomatic | Patient should be managed as per standard care, including implementation of additional glucose monitoring and initiation and/or increase of anti-hyperglycemic therapy (e.g., metformin). | Consideration should be given to suspending GDC-0032 (taselisib) dosing until the hyperglycemia resolves to Grade \leq 2. Dosing with GDC-0032 (taselisib) may resume at the same dose level or at one dose level lower as outlined in Table 1 and after discussion with the Study Principal Investigator. |
| 3, symptomatic (e.g., blurred vision, frequent urination, excessive thirst) or grade 4 | Patient should be managed as per standard care, including implementation of additional glucose monitoring and initiation and/or increase of anti-hyperglycemic therapy | GDC-0032 (taselisib) dosing should be suspended until the hyperglycemia resolves to Grade \leq 2. The patient will be discontinued from the study if such therapy fails to control their hyperglycemia. Dosing with GDC-0032 (taselisib) may otherwise resume at one dose level lower as outlined in Table 1. |

*Based on fasting glucose level

Management of Pneumonitis

Patients will be assessed for pulmonary signs and symptoms throughout the study (including physical examinations, pulse oximetry, and periodic CT scans). Oxygen saturation by pulse oximetry will be measured at every visit as part of the assessment of vital signs. Patients experiencing symptomatic or asymptomatic pneumonitis should be treated per standard of care and individual protocol guidelines adapted from recommendations by White et al. for the management of pneumonitis in cancer patients receiving everolimus¹⁰. Use of corticosteroids should be considered for symptomatic cases of noninfectious pneumonitis. Management guidelines for patients with possible pneumonitis are listed below in the Table 3

Table 3: Management of Pneumonitis

| Grade | Intervention | Investigations | Dose Adjustment |
|-------|--|---|---|
| 1 | No specific therapy required. | CT scan. Consider PFTs. Repeat CT scan every 6 to 9 weeks until return to baseline. | No change. |
| 2 | Symptomatic only. Prescribe corticosteroids ^a if cough is troublesome and infectious etiology is ruled out. | CT scan. Repeat CT scan every 4 weeks until return to baseline. Consider PFTs and bronchoscopy. | Discontinue all study treatment until improvement to Grade ≤ 1 . If pneumonitis improves to grade ≤ 1 and upon completion of any corticosteroids, resume GDC-0032 (taselisib) at one dose level lower Discontinue treatment if recovery to Grade ≤ 1 is not evident within 28 days. |
| 3- 4 | Prescribe corticosteroids if infectious etiology is ruled out. Taper as clinically indicated. | CT scan. Repeat CT scan every 4 weeks until return to baseline. Consider PFTs. Bronchoscopy is recommended. | Discontinue all study treatment regardless of the attribution. |

Table modified from White et al¹⁰.

^aSuggested corticosteroids include methylprednisolone dose pack or prednisone 60 mg daily followed by a taper (e.g., 60 mg \times 2 days, 40 mg \times 2 days, 20 mg \times 2 days, etc.).

CT = computed tomography; PFT = pulmonary function test

PFTs include tests for DLCO and room air oxygen saturation at rest (pulse oximetry).

Repeat CT scans should match schedule for re-staging exams if feasible.

Management of Rash

Treatment-related rash, including cases of Grade 3 rash, has occurred in patients who received GDC-0032 (taselisib) monotherapy or in combination with other anti-cancer drugs. This rash is commonly manifested as maculopapular type with or without pruritus, with some having developed desquamation. Rash and other dermatological events should be closely monitored. Patients with severe rash should be monitored for associated signs and symptoms, such as fever and hypotension that may be suggestive of a systemic hypersensitivity reaction. For severe rash, hold all study treatment until Grade ≤ 1 (see Table 4 below), and patients should be treated with supportive therapy per standard of care. Use of topical antihistamine, as well as topical or systemic corticosteroids, may be considered

Table 4: Dose Delay and Modification Guidelines for Rash

| Grade | Intervention | Dose Adjustment |
|--------------|--|---|
| Grade 1 | Consider prescribing topical corticosteroids ^a | Continue dosing at current dose and monitor for change in severity. |
| Grade 2 | Consider treatment with supportive therapy (e.g., topical or oral corticosteroids ^{a, b}). | Consider holding GDC-0032 (taselisib) or reducing to the next lower dose if rash is troublesome. |
| Grade 3 or 4 | Consider treatment with supportive therapy (e.g., topical or oral corticosteroids ^{a, b}). Consider dermatological consultation. Consider obtaining photographs of rash if permitted by local regulations. | Hold all study treatment until Grade ≤ 1 . Restart GDC-0032 (taselisib) at the next lower dose upon discussion with Overall Principal Investigator, or permanently discontinue. |

a Suggested topical steroids include, hydrocortisone 2.5% to face twice daily, triamcinolone 0.1% or fluocinonide 0.1% cream to body bid.

b Suggested oral steroids include methylprednisolone dose pack or prednisone 60 mg daily followed by a taper (e.g., 60 mg \times 2 days, 40 mg \times 2 days, 20 mg \times 2 days, etc.).

Management of Gastrointestinal Toxicity

Diarrhea

Patients should be closely monitored for gastrointestinal symptoms (e.g., nausea, vomiting, diarrhea, abdominal pain, stomatitis, and changes in stool, including checking for blood in stool if clinically indicated). Patients should be advised to inform the investigator if any diarrhea occurs, even if it is mild. Gastrointestinal symptoms should be managed per protocol guidelines. Prompt management of diarrhea with antidiarrheal medications should be implemented. Because of the approximately 40 hour half-life of GDC-0032 (taselisib), investigators should hold GDC-0032 (taselisib) for Grade ≥ 2 diarrhea.

Steroid-responsive diarrhea and colitis have been difficult to distinguish in patients treated with taselisib. All cases of colitis have been reversible with corticosteroid treatment. Prompt initiation of corticosteroids for persistent diarrhea despite anti-diarrheal treatment can decrease the severity of the diarrhea and prevent the need for hospitalization. Patients who develop severe steroid-responsive diarrhea usually have been on GDC-0032 (taselisib) treatment for at least 2 months, with an average onset at 4 to 6 months of treatment. A stool culture is helpful in identifying concurrent infections, and patients have been successfully treated with concurrent steroids and appropriate antibiotics, if needed.

If a patient is being treated with corticosteroids, total parenteral nutrition is discouraged, as this increases the risk for severe hyperglycemia. Discontinuation of non-steroidal inflammatory medications or other medications that exacerbate colitis are also recommended during colitis episodes.

Specific dose modification and management guidelines for diarrhea and colitis are provided in Table 5.

Colitis

For persistent Grade 2 diarrhea that does not resolve or for Grade ≥ 3 diarrhea, further evaluation should include colitis in the differential diagnosis with the appropriate work-up (e.g., abdominal CT scan, endoscopy with biopsy, stool cultures for cytomegalovirus, *Clostridium difficile*, and parasites). Grade ≥ 2 colitis should be managed by interruption of all study treatment. In addition, discontinuation of nonsteroidal anti-inflammatory medications or any other medications known to exacerbate colitis symptoms should be considered. If noninfectious colitis is suspected, treatment with corticosteroids per institutional standard of care is recommended. It is suggested that prednisone (for oral administration) or solumedrol (for IV administration) are the corticosteroids of choice in the treatment of colitis. For severe symptoms, prednisone 60 mg or equivalent may be required to control initial symptoms, and the dose should be gradually tapered. Lower doses of prednisone, oral budesonide, or mesalamine (or other 5-aminosalicylic acid derivatives) may be considered for less severe cases of colitis. It has been observed that patients that have developed colitis upon GDC-0032 (taselisib) treatment have improved with drug hold and coadministration of systemic steroids.

Specific dose modification and management guidelines for colitis are provided in Table 5.

Table 5: GDC-0032 (taselisib) Dose Modification and Management Guidelines for Diarrhea and Colitis

| Grade of Diarrhea | Intervention | Dose Modification |
|--------------------------------|---|--|
| Grade 1 | 
Manage per institutional standard of care that includes antidiarrheals.^a
 
For persistent Grade 1 diarrhea occurring after Cycle 2, recommend evaluation for infectious causes via stool culture^b. For non-infectious diarrhea, consider colonoscopy to evaluate for colitis.
 | Continue current dose. |
| Grade 2 | 
Initially manage per institutional standard of care until Grade \leq 1. These include antidiarrheals^a
 
Obtain stool culture for infectious workup^b
 
Infections (e.g. Clostridium difficile, enteric bacteria, CMV) should be treated with the appropriate antibiotic
 
For persistent Grade 2 non-infectious diarrhea lasting longer than 48 hours despite treatment with antidiarrheals, treat with oral corticosteroids (20-40 mg prednisone QD starting dose with taper) or budesonide 9mg PO QD.
 
If Grade 2 diarrhea does not improve after 48 hours of corticosteroid treatment, a colonoscopy is recommended to evaluate for other causes of diarrhea (e.g., CMV colitis)
 | 
Hold GDC-0032 (taselisib) and follow guidelines below:
 
If Grade 2 diarrhea occurred before Cycle 2, did not require corticosteroid treatment, and was an initial episode, resume GDC-0032 (taselisib) treatment at the same dose upon improvement to Grade \leq 1.
 
If Grade 2 diarrhea occurred after Cycle 2, was a recurrent episode, or improved with corticosteroid treatment, resume GDC-0032 (taselisib) treatment at one dose level lower upon improvement to Grade \leq 1 and after completion of corticosteroid treatment.
 
For Grade 2 colitis, resume GDC-0032 (taselisib) treatment at one dose level lower upon improvement to Grade \leq 1 and after completion of corticosteroid treatment.
 |
| Grade 3 (first episode) | 
Initially manage with antidiarrheals^a.
 
Obtain stool culture for infectious workup^b.
 
For Grade 3 diarrhea or colitis, treat with systemic corticosteroids (prednisone 60-80 mg QD equivalent or solumedrol 16-20 mg IV q 8 h to start). Can increase steroid dosage if diarrhea does not improve.
 
Concurrent infections (e.g., Clostridium difficile, enteric bacteria, CMV) should be treated with the appropriate antibiotic.
 
For patients that do not improve upon 48 hours of corticosteroid treatment, a colonoscopy is recommended to evaluate for other causes of diarrhea (e.g. CMV colitis)
 | Hold GDC-0032 (taselisib). If diarrhea or colitis improves to Grade \leq 1 and upon completion of any steroid taper or antibiotic treatment, resume GDC-0032 (taselisib) treatment at one dose level lower. |
| Grade 3 (recurrent) or Grade 4 | Work-up and treatment algorithm as for Grade 3 (first episode). | Permanently discontinue GDC-0032 (taselisib) |

a Suggested antidiarrheals include the following: 1) loperamide (initial: 4 mg, followed by 2 mg after each loose stool, up to 16 mg/day); 2) diphenoxylate and atropine (diphenoxylate 5 mg, four times daily [QID], until control achieved (maximum: 20 mg/day), then reduce dose as needed; some patients may be controlled on doses of 5 mg/day); 3) tincture of opium (6 mg of undiluted opium tincture (10 mg/mL) QID).

b Non-infectious diarrhea can be diagnosed by stool culture with work-up for various enteric bacteria and C. difficile. Fecal calprotectin is a possible marker for bowel inflammation. Blood-based CMV PCR test can also be used to detect CMV infection.

Management of Stomatitis and Oral Mucositis

Aggressive mouth care for oral mucositis and stomatitis with mouthwash formulations (e.g., combinations of local anesthetic, antihistamine, corticosteroid, antacid, antifungal and/or antibiotics) may also be helpful in managing symptoms, and it is recommended that these are implemented with early signs of dry mouth, Grade 1 mucositis, or Grade 1 stomatitis (see Table 6). Examples of mouth care include rinsing with nonalcoholic mouthwash, flossing after each meal, using a mild toothpaste and soft-bristled toothbrush, and avoiding agents containing hydrogen peroxide, iodine, and thyme derivatives. It may also be helpful to advise patients to avoid foods that are spicy, acidic, or salty.

Table 6: Dose Delay and Modification Guidelines for Stomatitis and Oral Mucositis

| Grade of Stomatitis/Mucositis | Intervention | Dose Adjustment |
|-------------------------------|--|---|
| Grade 1 | Aggressive mouth care that includes mouthwash formulations (e.g., combinations of local anesthetic, antihistamine, corticosteroid, antacid, antifungal and/or antibiotics) Diet management (e.g., avoidance of spicy foods) | Consider holding Taselisib until resolution before restarting at same dose. |
| Grade 2 | Aggressive mouth care that includes mouthwash formulations (e.g., combinations of local anesthetic, antihistamine, corticosteroid, antacid, antifungal and/or antibiotics) Diet management (e.g., avoidance of spicy foods) | Hold Taselisib and manage until Grade ≤ 1 then restart Taselisib at the same dose. If Grade 2 stomatitis/oral mucositis recurs, hold Taselisib until Grade ≤ 1 and restart Taselisib at the next lower dose. |
| Grade 3 or 4 | Aggressive mouth care that includes mouthwash formulations (e.g., combinations of local anesthetic, antihistamine, corticosteroid, antacid, antifungal and/or antibiotics) Diet management (e.g., avoidance of spicy foods) | Hold Taselisib and manage until Grade ≤ 1 then restart Taselisib at the next lower dose. For Grade 4 event, consider permanent discontinuation of Taselisib. |

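### Does Table 5 need rewriting because some Grade 2 diarrhea episodes fall under neither of its two resume rules?

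*Protocol*

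**What the plan says.** Protocol Section 3.4, Table 5, Grade 2 row, dose-modification column, first holds the drug and then gives three resume lines, each of which acts once the event has improved to Grade 1 or less.

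- Same dose: "If Grade 2 diarrhea occurred before Cycle 2, did not require corticosteroid treatment, and was an initial episode". All three conditions must be met.
- One level lower: "If Grade 2 diarrhea occurred after Cycle 2, was a recurrent episode, or improved with corticosteroid treatment". Any one condition is enough.
- Colitis: "For Grade 2 colitis, resume GDC-0032 (taselisib) treatment at one dose level lower", whatever the cycle or episode number.

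The intervention column of the same row adds: "If Grade 2 diarrhea does not improve after 48 hours of corticosteroid treatment, a colonoscopy is recommended".

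The text above Table 1 lets the investigator resume "at the same dose or at one dose level lower (as detailed in Tables 2–6"), depending on what the toxicity is and how severe it is. The same paragraph describes the Table 1 reductions as recommendations meant to keep benefiting patients on treatment, and the title of Table 5 also calls its contents guidelines. Below Table 1 stand two firm limits: "Dose re-escalation is not allowed after a dose reduction", and at the lowest level "if there is an indication for further dose reduction, the patient must permanently discontinue".

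**The concern.** A pair of resume rules should sort every recovered episode into exactly one branch. These two do not, for two reasons. Before and after Cycle 2 leave out Cycle 2 itself. Not requiring a corticosteroid and improving on one leave out the patient who received it without improving. The general permission to choose between two doses refers back to the tables, and Table 5 is silent on these events.

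Two investigators who both follow the text could therefore resume similar patients at different doses. Because re-escalation is barred, the lower choice would be permanent and would use one of only two reductions. For a patient already at the lowest level it would end treatment. Diarrhea is also the most common treatment-related event in the single-agent data of Section 1.2 (52% of 115 patients, any grade), so the row will be used.

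**Working it through.** **Inputs.** The three resume lines of Table 5; a cycle of 28 days (Schema), so Cycle 2 runs from day 29 to day 56; the dose levels of Table 1 (4 mg daily, 2 mg daily, 2 mg every other day, which averages 2/2 = 1 mg per day).

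**Step 1: literal enumeration.** Cross timing (Cycle 1, Cycle 2, later) with episode (initial, recurrent) and corticosteroid (not required, improved on it, not improved on it): 3 × 2 × 3 = 18 combinations.

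- Same-dose rule: 1 (Cycle 1, initial, not required).
- Lower-dose rule: 6 after Cycle 2, plus 6 recurrent in Cycle 1 or 2, plus 2 initial and improved on corticosteroid in Cycle 1 or 2 = 14.
- Neither: 18 − 1 − 14 = 3. These are Cycle 2, initial, not required; Cycle 1, initial, not improved; Cycle 2, initial, not improved.

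Adding colitis as a further factor leaves the same three uncovered, all without colitis.

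**Step 2: looser readings of the cycle boundary.** If after Cycle 2 means after it starts, one combination stays uncovered (Cycle 1, initial, not improved). If before Cycle 2 means up to its end, two stay uncovered (both of the not-improved ones). The two readings give opposite doses for the Cycle 2 episode without corticosteroid. No reading makes the rules exhaustive, so the gap is in the text.

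**Step 3: which combinations need a resume dose.** All three lines act only after improvement to Grade 1 or less. An episode that does not improve stays on hold, and no dose is due. The not-improved combinations matter only if the patient later recovers by another route, such as treatment of an infection, and colitis is not diagnosed. The 48-hour point triggers a colonoscopy; it does not finally classify the patient as a non-responder. Someone who improves on the corticosteroid after that point falls under the lower-dose rule. Setting aside the 6 not-improved combinations leaves 12: 1 same dose, 10 lower (4 after Cycle 2, 4 recurrent in Cycle 1 or 2, 2 initial and improved), 1 uncovered.

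**Step 4: what is at stake in the uncovered cases.** From the starting dose the choice is 4 mg or 2 mg daily. After one reduction it is 2 mg daily or an average of 1 mg per day. After two reductions it is the same dose or discontinuation. That last case needs two earlier reductions, with any holds and recoveries, before an initial Grade 2 diarrhea within the first 2 × 28 = 56 days, which is remote.

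**Step 5: timing evidence.** The diarrhea text of Section 3.4 says that severe steroid-responsive diarrhea usually appears after at least 2 months on drug, on average at 4 to 6 months. This concerns severe cases only, but it suggests that corticosteroid-treated episodes lie mostly after Cycle 2, where the lower-dose rule applies.

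**Step 6: the NOTE before the hyperglycemia guidance.** Its wording, "investigators should consider holding GDC-0032 (taselisib) for certain Grade 2 toxicities", is softer than the hold in the diarrhea text and in Table 5. It is no contradiction, because the NOTE defers to the specific text that follows, and no resume dose depends on it.

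**The case for a change.** The strongest case for a change is that discretion is not the protocol's default here. Where it wants judgment it says so: Table 2 leaves Grade 2 hyperglycemia to the investigator and states outright that asymptomatic Grade 3 may resume at either of two levels. The Grade 2 row of Table 5 has no such words, and the general sentence sends the reader back to it. Table 6 shows that a complete first-versus-recurrent rule is easy to write. The intervention column foresees failure to improve on a corticosteroid, while the column beside it never picks that patient up unless colitis is found. The remedy would be a few words in one row.

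Much of this stands. The text assigns no dose to the Cycle 2 episode, and the discretion clause does not supply one. What does not follow is that the gap does harm. Section 3.4 accepts different choices by different investigators elsewhere: asymptomatic Grade 3 hyperglycemia (after discussion with the study principal investigator), and holding or reducing for troublesome Grade 2 rash. The cost of the remedy is small, but no gain to safety or to interpretation of the results has been shown.

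**Conclusion.** This is missing detail in management guidance, and investigators can fill it within the limits the protocol sets. One combination of the 12 in Step 3 is literally uncovered, and a second, narrower case arises only when a non-colitis episode recovers by a route other than the corticosteroid. In both, the available choices are the two that Section 3.4 already names. No stated rule gives a wrong dose or conflicts with another on this point, and nothing in eligibility, sample size, endpoint or analysis depends on it. The pill calendar (Appendix I) records the tablets taken each day, so the dose actually resumed will be known.

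The conclusion rests on two assumptions: that the tables are applied as guidelines, as Section 3.4 and the title of Table 5 describe them, and that the uncovered episodes are not so common as to shift dosing across the planned 70 patients. The protocol gives no Grade 2 or by-cycle frequency, so the second cannot be quantified. Which dose fits these episodes is a clinical question on which this review takes no position.
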